#### 6.2.5.10 Fried Index

The Fried Index is a measure of frailty (33). It is composed of 5 criteria:

- Self-reported unintentional weight loss of  $\geq 10$  pounds or 5% in the prior year (should be verified with medical records if possible)
- Reduced grip strength (<23 lbs. for women, <32 lbs. for men as measured in the dominant hand using a dynamometer; this is averaged over 3 assessments)
- Self-reported exhaustion (person states they are exhausted 3 or more days per week; exhaustion is feeling “everything I do is an effort” or “sometimes I just cannot get going”)
- Reduced gait speed (>0.8 m/sec over 4 meters; this is averaged over 2 assessments)
- Self-reported low physical activity (being “limited a lot” in vigorous activities from the SF-36 form)

One point is given to each positive criterion with zero points indicating no frailty, 1-2 points indicating pre-frailty, and 3-5 points indicating frailty.

The Fried Index will be assessed only at the Entry Visit.

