### 1.3 Study II Primary Objectives

1.3.1 To compare FRAIL scale, Fried Index, and SPPB scores between those with ISI scores  $\geq 11$  and those with ISI  $< 11$ .

1.3.2 To compare CSRQ-25 and Digit Symbol Substitution Test (DSST) scores between those with ISI scores  $\geq 11$  and those with ISI  $< 11$ .

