### 1.4 Study II Secondary Objectives

1.4.1 To correlate ISI scores with each of the following: PSQI, PHQ-9, SF-36, WHOQOL-HIV Brief, FRAIL scale, Fried Index, SPPB, CSRQ-25, and DSST.

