## 2.0 HYPOTHESES, BACKGROUND, AND INTRODUCTION

### 2.1 Hypotheses

2.1.1 Treatment with SHUTi will reduce ISI, PSQI, PHQ-9, SF-36, and WHOQOL-HIV Brief scores at 10 weeks when compared to UC.

2.1.2 HIV-infected patients with ISI scores  $\geq 11$  will have higher FRAIL scale, Fried Index, and SPPB scores and lower CSRQ-25 and DSST scores compared to those with ISI scores  $< 11$ .

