#### 6.2.5.11 Short Physical Performance Battery (SPPB)

The SPPB assesses physical functioning and includes standing balance (3 stances), walking speed, and sit-to-stand test time. Each task is rated from zero (indicating inability to complete the task) to four points (indicating best performance) based on established criteria (33), and results from the 3 tasks are summed. Standing balance is measured by a hierarchical performance scale based on side-by-side stance, “semi-tandem” stance (heel to 1st MTP joint), and full tandem (heel to toe), with each stance being held up to for ten seconds. Walking speed is measured in m/sec based on the faster of two 4-m walks at usual pace. Sit-to-stand test time is assessed by the time required to perform five uninterrupted repetitions of sit-to-stand using a firm chair and without use of the arms. An SPPB score of less than 9 is highly predictive for subsequent disability and is considered low function, 9–11 points moderate function, and 12 points (no deficits) high function. A standardized scoring sheet (see Appendices) will be used for this assessment.

The SPPB will only be assessed at the Entry Visit.

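### The Fried Index gait item is labelled as slow walking but gives the frailty point for walking faster than 0.8 m/sec, reversing one scored item of a Study II primary measure

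*Combined protocol and SAP*

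**What the plan says.** Section 6.2.5.10 lists five Fried criteria. The gait criterion reads "Reduced gait speed (>0.8 m/sec over 4 meters; this is averaged over 2 assessments". The other criterion worded as a reduction reads "Reduced grip strength (<23 lbs. for women, <32 lbs. for men as measured in the dominant hand using a dynamometer". The scoring rule is "One point is given to each positive criterion with zero points indicating no frailty, 1-2 points indicating pre-frailty, and 3-5 points indicating frailty", so more points mean more frailty.

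Section 6.2.5.11 uses the same physical quantity for the SPPB: "Walking speed is measured in m/sec based on the faster of two 4-m walks at usual pace". There each task earns up to four points for best performance, and the top of the total scale is "12 points (no deficits) high function".

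The Fried Index is a Study II primary measure (1.3.1: "To compare FRAIL scale, Fried Index, and SPPB scores between those with ISI scores" at or above 11 and below 11). It is also one of the variables in 1.4.1 ("To correlate ISI scores with each of the following"). Hypothesis 2.1.2 expects that participants with insomnia "will have higher FRAIL scale, Fried Index, and SPPB scores".

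**The concern.** Label and rule in the gait item point in opposite directions. Read literally, a fast walk counts as good on the SPPB and as a sign of frailty on the Fried Index.

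The plan offers no second source that would settle it. The SPPB and DSST sections refer to a scoring sheet and a scoring template; the Fried section refers to neither, so its text is the only visible scoring rule. The study team builds the REDCap database (9.15) and is responsible for the analysis (9.1), and a programmer who follows the text would code the printed sign. Automated range checks would not catch the error, because a reversed 0/1 item is still in range.

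At stake are the individual Fried totals, the reported levels of frailty, the primary comparison in 1.3.1 and the correlation with ISI in 1.4.1. Section 2.3 says these frailty data are wanted to justify later trials.

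A lesser wording point goes with this. Hypothesis 2.1.2 puts SPPB among the scores expected to be higher with insomnia, although a higher SPPB is better function. That changes no score and no two-sided comparison; it affects only whether a result is read as supporting the hypothesis.

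**Working it through.** **Inputs from the documents.** The gait label and rule, one point per criterion, and categories 0 / 1–2 / 3–5 (6.2.5.10); Study II groups of 32 and 12, so 32 + 12 = 44 (3.1, 10.2.1). The plan has no sample size, power or effect figure that depends on this item, so there is none to reproduce.

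**Inputs the documents do not give.** The proportion of slow walkers and the prevalence of the other four criteria. Values used for these below are assumptions.

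**Step 1: direction.** The unit is m/sec, so a value above 0.8 is faster. A greater-than sign would suit a walking time (4 m ÷ 0.8 m/sec = 5 seconds, longer being slower), but the item is not stated as a time. No reading reconciles label and rule.

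**Step 2: individual score.** Let K be the total of the other four criteria and S = 1 if mean speed is below 0.8 m/sec, otherwise 0.
- Score matching the label: K + S.
- Score as printed: K + (1 − S).
- Printed minus label: 1 − 2S, which is +1 for a fast walker and −1 for a slow one.

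At exactly 0.8 m/sec both strict inequalities give 0, so there is no difference. Everyone else is wrong by one point, whatever the distribution of speeds.

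**Step 3: category.**

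| K | Fast walker: label → printed | Slow walker: label → printed |
|---|---|---|
| 0 | none → pre-frail | pre-frail → none |
| 1 | pre-frail → pre-frail | pre-frail → pre-frail |
| 2 | pre-frail → frail | frail → pre-frail |
| 3 | frail → frail | frail → frail |
| 4 | frail → frail | frail → frail |

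The category is wrong only for K = 0 and K = 2.

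**Step 4: how many categories.** Assume the other four criteria are independent, each with prevalence q. Then P(K = 0 or 2) = (1 − q)⁴ + 6q²(1 − q)².

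| q | P(K=0) + P(K=2) | Of 44 |
|---|---|---|
| 0.1 | 0.6561 + 0.0486 = 0.705 | 31.0 |
| 0.2 | 0.4096 + 0.1536 = 0.563 | 24.8 |
| 0.3 | 0.2401 + 0.2646 = 0.505 | 22.2 |
| 0.4 | 0.1296 + 0.3456 = 0.475 | 20.9 |

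**Step 5: group means.** In a group with slow-gait proportion p, the mean moves by 1 − 2p: +0.90 for p = 0.05, +0.80 for 0.10, +0.60 for 0.20, +0.40 for 0.30. With p1 (insomnia) and p0 (no insomnia), a true difference d becomes

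d + (1 − 2p1) − (1 − 2p0) = d − 2(p1 − p0).

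| p1 − p0 (assumed) | Change in group difference |
|---|---|
| 0 | 0 |
| 0.05 | −0.10 |
| 0.10 | −0.20 |
| 0.15 | −0.30 |
| 0.20 | −0.40 |

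The gait item's own contribution changes sign: with p1 = 0.20 and p0 = 0.10 it goes from +0.10 to −0.10. If gait supplies a share s of d, the printed difference is (1 − 2s) times the true one. For s = 0.2 that is 60%, for example 0.50 − 2 × 0.10 = 0.30. For s = 0.5 it is zero, and only for s above 0.5 does the total difference reverse.

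**Step 6: correlation with ISI.** The covariance Cov(ISI, K + S) becomes Cov(ISI, K) − Cov(ISI, S), a change of −2 Cov(ISI, S). It vanishes only if slow gait is uncorrelated with ISI.

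**The case against.** The strongest reply is that this is probably a typographical slip. The label, the purpose of the index and the sign on the grip item all point one way, so a trained scorer may well apply the intended rule. No Fried scoring form or program is visible, and mis-scoring is not shown. That stands, and everything above is conditional on the printed sign being used.

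Second, the one-point error largely cancels in the comparison if slow gait is rare or equally common in both groups. That is plausible: adults are enrolled from age 18, and vascular disease, heart failure and disorders that impede the procedures are excluded (4.2.4, 4.2.5, 4.2.13). This also stands for the group difference, which does not move when p1 = p0. It does not rescue the individual totals, the categories or the reported level of frailty.

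Third, 1.3.1 compares scores, not categories, and independence of the four other criteria is doubtful for components of one index. The category counts are therefore illustrative and should not carry the argument.

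Fourth, the stakes are modest. This is a pilot in which significant differences are not expected (9.2), FRAIL and SPPB are untouched, and the error can be reversed. The pilot status cuts both ways: where testing is not the aim, the scores and estimates are the product, and those are what a reversed item corrupts. That the error is easy to reverse is a reason to correct it now.

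**Conclusion.** The concern holds. As written, the gait criterion contradicts its own label and reverses one of five scored items in a Study II primary measure; it must be corrected before scoring. If the printed sign is applied, every Fried total is wrong by one point except at exactly 0.8 m/sec. That result needs no assumption about the participants.

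The effect on the group difference is −2(p1 − p0): nil if slow gait is equally common in both groups, and 0.10 to 0.40 points for an assumed gap of 0.05 to 0.20. Under the assumed independent prevalences of 0.1 to 0.4 for the other criteria, about 31 down to 21 of 44 participants would be put in the wrong frailty category. Whether any score has actually been affected cannot be judged from the documents. The severity rests on the gait rule alone, not on the SPPB wording. Study I and its ISI outcome are not affected.

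**What to change.** - In 6.2.5.10, make the inequality agree with the label, so that the point is given when the mean of the two walks is below the cut-off. State how a mean of exactly 0.8 m/sec is scored.
- Before scoring, check the sign, unit and cut-off against the source the protocol cites for the index (reference 33) and against the case report form or score program.
- Keep both walk speeds on the form, because the Fried item averages two assessments while the SPPB takes the faster of two walks.
- Re-score any recorded speeds. If only the gait point was stored under the printed sign, the corrected point is 1 minus the stored point. The exception is a speed of exactly 0.8 m/sec, which a strict less-than rule scores 0.
- As a wording correction, move SPPB in 2.1.2 from the scores expected to be higher to those expected to be lower. No position is taken on CSRQ-25, whose scoring direction the documents do not describe.

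The cost is one sign, one wording change and a check of the form or program. No new data are needed.

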#### 6.2.5.11 Short Physical Performance Battery (SPPB)

The SPPB assesses physical functioning and includes standing balance (3 stances), walking speed, and sit-to-stand test time. Each task is rated from zero (indicating inability to complete the task) to four points (indicating best performance) based on established criteria (33), and results from the 3 tasks are summed. Standing balance is measured by a hierarchical performance scale based on side-by-side stance, “semi-tandem” stance (heel to 1st MTP joint), and full tandem (heel to toe), with each stance being held up to for ten seconds. Walking speed is measured in m/sec based on the faster of two 4-m walks at usual pace. Sit-to-stand test time is assessed by the time required to perform five uninterrupted repetitions of sit-to-stand using a firm chair and without use of the arms. An SPPB score of less than 9 is highly predictive for subsequent disability and is considered low function, 9–11 points moderate function, and 12 points (no deficits) high function. A standardized scoring sheet (see Appendices) will be used for this assessment.

The SPPB will only be assessed at the Entry Visit.

#### 6.2.5.12 Digit Symbol Substitution Test (DSST)

The DSST is a sensitive measure of dementia. The DSST requires that the participant fill in a series of symbols correctly coded within 90 seconds. The higher the score, the better the performance. This test requires a pencil with eraser, stop watch, DSST task sheet, and scoring template (see Appendices). The test will be administered in a quiet environment at a desk or table.

The DSST will only be administered at the Entry Visit.

### 7.0 ADVERSE EVENT MANAGEMENT

Although not an inherent risk of the study intervention or study procedures, participants for this study may have depression as determined through completion of the PHQ-9 questionnaire. As such, these participants may have suicidal ideation at screening or develop suicidal ideation during the course of the study. We have already put into place a protection protocol for just this event in our ongoing studies in HIV-infected and HIV-uninfected depressed patients (please see Appendix at end of this protocol). If a participant reports having thoughts of being better off dead or of hurting him/herself (i.e., responds with a 1, 2, or 3 to PHQ-9 Item #9 or spontaneously reports suicidal ideation), the visit will be immediately stopped, and the research assistant will interview the participant to complete the Patient Suicidality Form (see Appendix). If the participant answers “no” to all three suicide questions or if the patient answers “yes” only to Question 3 (previous attempt) and the most recent attempt was  $\geq 10$  years ago, the visit will proceed as normal, and the completed Patient Suicidality Form will be given to the principal investigator.

If the participant answers “yes” to any of the three questions (for Question #3 the previous attempt must be within the past 10 years), the research assistant will immediately contact the principal investigators. [name] (a clinical psychologist) and [name] (a physician) will review the case as soon as possible, but no later than the same day, to determine the appropriate course of action (e.g., immediately contact the patient’s primary care provider, primary HIV provider, clinical social worker, or care coordinator, consult with clinicians at Midtown Community Mental Health Center, and/or escort the patient to the Crisis Intervention Unit at Eskenazi Health). Additional authorities, including the police, may be contacted if immediate harm is of concern. Participants may be withdrawn from the study.

A direct correspondence by phone call and letter (both an email and a hard copy version), will also be sent to the potential participant’s primary provider notifying him/her of the situation (see below).

If an enrolled participant reports having thoughts of being better off dead or of hurting him/herself during any telephone calls (e.g., a scheduling call or a call to the study team initiated by the participant), the exact same procedures as outlined above will immediately be initiated. Please see the Appendix for the full Suicide Management Plan.

Since it is unknown if depression therapy (or lack thereof) results in somatic adverse events in antiretroviral-treated HIV-infected patients, we will also carefully document Grade 3 or 4 level toxicities defined using the Division of AIDS Table for Grading Adult Adverse Experiences. Clinical management decisions and decisions to discontinue participants from the trial will be made by the principal investigator(s) in conjunction with the participant's primary caregiver; care plans and outcomes must be included in the source documentation.

All serious adverse events (SAEs) will be documented on CRFs with unexpected SAEs forwarded to the IUPUI IRB within 10 working days of the event and the remainder to be documented on the annual continuing review.

## 8.0 CRITERIA FOR STUDY DISCONTINUATION

- Request by the participant to withdraw
- Request of the primary care provider if s/he believes the study is no longer in the best interest of the participant
- If the participant is found to be pregnant or begins breastfeeding during the course of this study
- If the participant has develops fever, need for systemic therapy for acute or serious illness, or hypotension after screening that precludes completion of the study visits within the allowed timeframes
- Requirement for prohibited concomitant medication(s)
- Clinical reasons believed life threatening by the physician
- Participant, as judged by the investigators, to be at risk of failing to comply with the provisions of the study protocol as to cause harm to self or interfere with the validity of the study results

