### 4.2 Exclusion Criteria

- 4.2.1 Inability to complete written, informed consent.
- 4.2.2 Incarceration at the time of any study visit.
- 4.2.3 Active suicidality, as determined by the patient's HIV provider or social worker following a positive response (1, 2, or 3) to PHQ-9 Item #9 and a positive response (yes) to one or more of the three questions (for Question #3, the previous attempt must be within the past 10 years) on the Patient Suicidality Form (see Appendix).
- 4.2.4 Diagnosed vascular disease (documented history of angina pectoris, coronary disease, peripheral vascular disease, cerebrovascular disease, aortic aneurysm, or otherwise known atherosclerotic disease).
- 4.2.5 History of congestive heart failure, even if currently compensated.
- 4.2.6 Diagnosed disease or process, besides HIV infection, associated with increased systemic inflammation (including, but not limited to, systemic lupus erythematosus, inflammatory bowel diseases, other collagen vascular diseases).

Note: Hepatitis B or C co-infections are NOT exclusionary

- 4.2.7 Known or suspected malignancy requiring systemic treatment within 180 days of the Entry Visit.

NOTE: Localized treatment for skin cancers is not exclusionary.

- 4.2.8 Therapy for serious medical illnesses within 14 days prior to screening.

Note: Therapy for serious medical illnesses that overlaps with a main study visit will result in postponement of that study visit until the course of therapy is completed; postponement outside of the allowed study visit timeframe will result in study discontinuation.

- 4.2.9 Pregnancy or breastfeeding during the course of the study.

- 4.2.10 Receipt of investigational agents, cytotoxic chemotherapy, systemic glucocorticoids (of any dose), or anabolic steroids at the Entry Visit.

Note: Physiologic testosterone replacement therapy or topical steroids is not exclusionary. Inhaled/nasal steroids are not exclusionary as long as the participant is not also receiving HIV protease inhibitors.

- 4.2.11 Active drug use or dependence that, in the opinion of the investigator, would interfere with adherence to study requirements.

- 4.2.12 History of schizophrenia, bipolar disorder, or dementia.

NOTE: Depression is not exclusionary as long as the severity of depression does not impede ability to perform the required study procedures.

- 4.2.13 Musculoskeletal or neurologic disorders that impede ability to perform the required study procedures.

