#### 9.5 Analysis Datasets

Datasets	Definition
Intention-to-treat (ITT)	This will comprise all patients who meet the eligibility criteria and are randomized onto the study irrespective of their compliance to the planned course of treatment.
Per Protocol Set	This will comprise all UC patients and SHUTi participants.
Safety	This will comprise the SHUTi patients that attend at least one session of treatment.

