#### 9.7 Disposition

The number of enrolled subjects will be summarized in a flow chart with frequency of completion and discontinuation. The subjects discontinued from SHUTi and their corresponding information will be listed. Significant protocol violations will be tabulated and/or listed.

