#### 9.10 Analysis Plan for the Primary Objective

To test our primary hypothesis, an analysis of covariance (ANCOVA) will be performed to test for treatment group differences in Week 10 ISI adjusted for baseline ISI using the intent-to-treat set. Statistical significance will be considered if two-sided p-value  $<0.05$ . This analysis will be also repeated using the per-protocol set.

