#### 9.14 Missing Data

Multiple imputations will be adopted to account for missing data. If differential missing patterns are observed, sensitivity analyses will be performed to evaluate the consequences of potential missing mechanisms.

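### Participants are discontinued from the study with no statement that the Week 10 ISI is still sought, and the check on the imputation depends on an undefined trigger that bias need not set off

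*Combined protocol and SAP*

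**What the plan says.** Section 8.0 lists seven criteria for discontinuation from the study. One is the participant's own request. The other six are provider request, pregnancy or breastfeeding, illness ("need for systemic therapy for acute or serious illness, or hypotension after screening that precludes completion of the study visits within the allowed timeframes"), need for a prohibited medication, life-threatening clinical reasons, and the investigators' judgement that the participant may not comply. The note to 4.2.8 adds that, for therapy of a serious illness that overlaps a main visit, "postponement outside of the allowed study visit timeframe will result in study discontinuation". Neither place separates stopping SHUTi from leaving the study, and neither mentions later outcome collection.

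Section 9.5 keeps eligible randomised patients in the ITT set "irrespective of their compliance to the planned course of treatment". Section 9.10 tests "treatment group differences in Week 10 ISI adjusted for baseline ISI using the intent-to-treat set".

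Section 9.14 adopts multiple imputation without naming a model or an assumption, and then says: "If differential missing patterns are observed, sensitivity analyses will be performed to evaluate the consequences of potential missing mechanisms".

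Under section 9.7, enrolled subjects are "summarized in a flow chart with frequency of completion and discontinuation". For individual detail it says: "The subjects discontinued from SHUTi and their corresponding information will be listed".

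**The concern.** Two gaps meet here.

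First, a participant can be taken out of the study for a reason that does not stop them answering a short questionnaire. Pregnancy or breastfeeding, a prohibited medication and a judged risk of non-compliance are the clearest cases. The illness criterion is a weaker example, because it concerns people who cannot complete visits in the window. If the team reads discontinuation as the end of data collection, a primary outcome that could have been observed is imputed instead.

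Second, the plan tests the imputation only when the observed missingness looks differential. It does not say whether that means counts, reasons or timing, or what size would count. Observed patterns cannot show whether the unseen scores differ from the imputed ones, and bias does not need unequal numbers missing. A comparison of reasons between arms is not a planned output either, because section 9.7 lists participant detail for SHUTi only.

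What is at stake is the effect estimate. Section 9.2 does not expect significance. It rests the pilot's value on successful implementation and on effect sizes that are clinically relevant. As written, no analysis is certain to show how far that effect size depends on the imputation.

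**Working it through.** **Inputs from the documents.** 16 per arm (section 3.1); 25% expected dropout and about 12 completers per arm (section 9.2); ITT ANCOVA on Week 10 ISI adjusted for baseline (section 9.10).

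**The plan's own figure.** 16 × (1 − 0.25) = 12 per arm, which matches section 9.2. So 4 of 16 primary outcomes per arm, 8 of 32 in all, are expected to be missing from all causes.

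**Assumptions, none of them in the documents.** How much worse the missing participants are than imputed (s, in ISI points); a completer effect of 4 points; an ISI SD of 5 (range 4 to 6); a baseline to Week 10 correlation of 0.5 (range 0.7 to 0.3); the rate of section 8.0 removals.

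**Bias formula.** Lower ISI is better. If a share m of an arm is missing and those people are truly s points worse than imputed, the arm's true mean is m × s above its imputed mean. With 1 = SHUTi and 0 = UC:

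overstatement of the SHUTi benefit = m1 × s1 − m0 × s0

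| Missing per arm | s1 = 4, s0 = 0 | s1 = 4, s0 = 4 | s1 = 4, s0 = 6 | s1 = 0, s0 = 4 |
|---|---|---|---|---|
| 1 of 16 | +0.25 | 0 | −0.125 | −0.25 |
| 2 of 16 | +0.5 | 0 | −0.25 | −0.5 |
| 4 of 16 | +1.0 | 0 | −0.5 | −1.0 |

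For one missing per arm, a reported effect of 4 would stand against a true 3.75 (0.25/3.75 = 6.7% overstated) or a true 4.25 (0.25/4.25 = 5.9% understated). Unequal counts with equal s = 4 also bias: 4 v 2 missing gives (4/16 − 2/16) × 4 = +0.5, and 2 v 4 gives −0.5.

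**Simulation check.** 16 per arm, 4 missing in each, completer effect −4, SD 5, correlation 0.5, 20 imputations under missing at random, ANCOVA, 3,000 trials (Monte Carlo SE 0.03). For (s1, s0) = (4,0), (4,4), (4,6), (0,4) the overstatement was 0.94, 0.03, −0.49 and −1.00. The formula gives 1.0, 0, −0.5 and −1.0.

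**Could the trigger catch it?** If it were read as a Fisher test on dropout counts, which is only one possible reading, the two-sided p would be 1.00 for 4 v 4, 0.69 for 5 v 3, 0.22 for 6 v 2 and 0.037 for 7 v 1. At 4 v 4 a rule based on counts cannot fire, yet the bias can be ±1.0 under the departures above.

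**Random error for scale.** 95% half-width = t(2n − 3) × SD × √(1 − r²) × √(2/n).
- n = 12, SD 5, r = 0.5: 3.68 points.
- n = 12 over the assumed range: 2.43 (SD 4, r = 0.7) to 4.86 (SD 6, r = 0.3).
- Relative to 3.68, a bias of 0.25 is about 7% and a bias of 1.0 about 27%.

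**If scores were recovered.** Suppose 2 of the 4 missing per arm were obtained (an assumption). The share missing falls from 4/16 to 2/16, so the bias halves, and the half-width at n = 14 is 3.37, about 8% narrower.

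**The case against.** The strongest reply is that the effect is small. The documents give no rate for section 8.0 removals. One per arm moves the estimate by at most 0.25 points even with a 4-point departure in one arm and none in the other, and section 9.2 sets no numeric threshold that such a shift would cross. The 1.0-point figure uses all-cause dropout, of which discontinuations under section 8.0 are only some part. This stands, and it limits the weight of the point.

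It is also fair that missing data are not ignored. Multiple imputation is planned, the condition in 9.14 is worded broadly enough to take in reasons and timing, and section 9.1 allows exploratory analyses. None of these is a commitment to test the imputation. The per-protocol set in section 9.5 does not help, because as worded it takes in both arms in full.

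Some section 8.0 cases could not or should not be contacted, such as those with life-threatening reasons. That stands, and the fix allows for it.

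Three stronger readings are tempting, and the documents do not support them.
- A reader might infer that these participants' outcomes are certainly lost. The documents are silent; they do not say collection stops. New diagnoses and medications are recorded at the Week 10 Visit (section 6.1), so some UC cases may first surface when the ISI is being completed anyway.
- A reader might infer that the SHUTi benefit will be overstated. The removal reasons can arise in either arm, and the bias can run either way or cancel.
- A reader might infer that online forms already allow remote completion. Section 6.2.6.6 provides them at the study visits only.

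**Conclusion.** The point holds as a gap in outcome follow-up combined with a sensitivity analysis tied to the wrong condition. It should be fixed, but it does not invalidate the trial.

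At the planned 25% dropout the ITT effect could be off by up to 1.0 ISI point in either direction with no planned analysis certain to show it. This rests on an assumed 4-point departure from the imputed values in one arm only; equal departures in arms with equal missingness give zero. Section 8.0 removals alone would matter less, at most 0.25 points for one per arm. All of these are smaller than the random error of about 3.7 points. The confidence interval is no substitute, though: it does not show how far the estimate depends on the imputation assumption.

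**What to change.** Leave every clinical stopping criterion and the visit-postponement rule unchanged, and amend the following.

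- **Section 8.0 and the 4.2.8 note.** State that discontinuation does not by itself end collection of the Week 10 ISI. Seek it in the 63 to 84 day window from every randomised participant who has not withdrawn consent to data collection, where contact is practicable, by phone if needed. Section 3.2 already gives the ISI by phone at screening. Flag scores taken by phone or during therapy for a serious illness, and report the primary result with and without them.
- **Section 9.14.** Drop the condition. Always report a delta-adjusted imputation with deltas varied separately in each arm (for example 0, 2, 4 and 6 points), read as a range beside the main estimate. Imputing from UC alone would leave the UC arm at missing at random and so test only one direction.
- **Section 9.7.** List discontinuation reasons for both arms.

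The cost is a few phone questionnaires and some SAP wording. There are downsides. A few scores will be of mixed mode, and some may reflect an acute illness. With about 4 imputed values per arm, the delta analysis is driven by its assumptions. Participants who withdraw consent or are lost to follow-up are not recovered.
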